4.3. Final sample size

Total number = 250 (Wolverine cutting balloon = 125, Non-compliant balloon = 125)

5. Methods

5.1. PCI procedure and medication:

PCI and stent implantation will be performed according to the current guidelines using standard interventional techniques (reference). Before PCI, all patients will be administered loading doses of aspirin (200–300 mg), clopidogrel (300–600 mg), ticagrelor (180 mg), or prasugrel (60 mg). After sheath insertion at the arterial access site, weight-adjusted unfractionated heparin will be administered at a bolus dose of 100 U/kg, with an additional bolus to maintain an activated clotting time of 250–300 s. Additional intravenous and intracoronary injections of platelet glycoprotein IIb/IIIa receptor blockers will be administered at the discretion of the operator. The interventional strategy, balloon size, and stent selection will be based on the discretion of the same operator for all patients. However, modification of the calcific atheroma using rotational atherectomy can be performed at the operator's discretion in cases of balloon-uncrossable lesions, and these cases will be excluded from enrollment. All patients who undergo PCI will receive aspirin (100 mg daily) with clopidogrel (75 mg daily), ticagrelor (180 mg), or prasugrel (60 mg) because a dual antiplatelet

maintenance regimen for at least 12 months is recommended. Cilostazol (100–200 mg daily) will be administered as an adjunct to the dual antiplatelet regimen at the treating physician's discretion. In-hospital stay and after-discharge medications include aspirin, clopidogrel, ticagrelor, prasugrel, beta-blockers, calcium channel blockers, angiotensin-converting enzyme inhibitors, angiotensin receptor blockers, and lipid-lowering agents such as statins, which will be recorded and entered into a dedicated computerized database with clinical information.

5.2. Quantitative coronary angiography:

Coronary angiography will be digitally recorded at baseline and immediately after the procedure (post-balloon and post-stenting) and assessed offline in the angiographic core laboratory. The quantitative coronary angiographic analysis will be performed using an automated edge-detection algorithm (CAAS-5; Pie-Medical, Best, Netherlands) with conventional methods by independent interventional cardiologists who are blinded to the type of balloon used, treatment outcomes, and IVUS analysis. All measurements will be performed using cineangiograms recorded after the intracoronary injection of nitroglycerin. The interpolated reference diameter will be considered as the reference segment diameter. The lesion length is defined as the distance from the proximal shoulder to the distal shoulder at the lesion site. Standard qualitative and quantitative analyses and definitions will be used for quantitative coronary angiography (QCA) (qca 1, 2 references).

5.3. IVUS procedure and analysis:

After regular coronary angiography, IVUS will be performed at baseline (before pre-dilatation) and repeated immediately after stent implantation in all cases. IVUS will be performed using an OptiCross 60 MHz (Scientific Corporation, Maple Grove, MN, USA). After intracoronary injection of nitroglycerin, the IVUS catheter will be carefully advanced distal to the culprit lesion under fluoroscopic guidance and then withdrawn automatically at 0.5 mm/s to perform the imaging sequence, which begins 20 mm distal to the culprit lesion and ends at the aorto-

ostial junction. IVUS imaging will be recorded on the compact disc for offline analysis by a single experienced observer who is unaware of the clinical and angiographic information. IVUS measurements will be performed in accordance with the American College of Cardiology Clinical Expert Consensus Document on the Standards for Acquisition, Measurement, and Reporting of Intravascular Ultrasound Studies. The ischemia-related vessel is identified as narrow ($\geq 70\%$) using angiography. The culprit lesion site selected for analysis is the image slice with the lowest luminal cross-sectional area (CSA). The proximal and the distal reference segments are defined as the most normal-looking cross-sections within the same arterial segment, typically ≤ 10 mm from the lesion, but before any large side branch.

We will measure the lumen in the minimum lumen area slice. The lumen CSA will be measured every 1 mm of the culprit lesion segment, and the average lumen CSA will be calculated. The maximum calcium arc, calcium length, and calcium ratio (calcium length/lesion length) will be measured. After stent implantation, we will measure the minimum stent CSA, minimum and maximum stent diameters, and acute CSA gain. Acute CSA gain = minimum stent CSA - minimum CSA. Stent symmetry = minimum stent diameter/maximum stent diameter. Stent expansion = minimum stent CSA/reference lumen CSA. Incomplete stent apposition is defined as insufficient close contact between the struts and the underlying wall. Stent asymmetry is defined as stent symmetry of at least one section < 0.7 . Stent under expansion is defined as a stent expansion rate of < 0.8 .

6. Study device

- 1) Wolverine (Boston Scientific, Natick, MA, USA) cutting balloon
- 2) bioabsorbable polymer-coated everolimus-eluting coronary stent (Synergy™, Boston Scientific Corporation, Marlborough, MA, USA)
- 3) NC balloon (the type of NC balloon will be decided at the operator's discretion)
- 4) IVUS will be performed using an OptiCross 60 MHz (Scientific Corporation, Maple Grove, MN, USA).

7. Study Population

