[figure not shown]

Study Title	
Assessment of Cutting-Balloon Angioplasty with Novel Bioabsorbable Polymer-Coated, Everolimus-Eluting Stent in the Treatment of Calcified Coronary Lesions Guided by Intravascular Ultrasound: Study Design and Protocol

Study Title (Short Description)	
CUPID trial

Principle Investigator	
[name]., PhD.

Institution Name & Location	
SoonChunHyang University Hospital [name]

Contact information	
Email: [contact] [contact] [contact]

1. Study protocol

Novel cutting balloon prospective, randomized, open-label, multi-center study

This clinical trial is designed as a prospective, observational, open-label, multi-center trial that will investigate the noninferiority of cutting balloon pre-dilatation compared with NC-balloon pre-dilatation in the treatment of calcified lesion who underwent bioabsorbable polymer-coated, everolimus-eluting coronary stent implantation.

Planned number of sites: 5 institutions in South Korea

1. SoonChunHyang University Hospital, Bucheon
2. SoonChunHyang University Hospital, Cheonan
3. Eulji Medical Center, Eulji University, Daejeon
4. Seoul St.Mary's Hospital, Seoul
5. Hanil General Hospital, Seoul

2. Study Outcomes

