5.2. Secondary endpoint: comparing the clinical outcomes

- ① MACE (major adverse cardiac events): composite of death, MI, TVR at 1yr follow-up
- ② TLR (target lesion revascularization) at 1yr follow-up
- ③ Procedure time, the total amount of contrast, and the number of balloons

3. Analysis plan

- 6.1. Study period: 24 months
- 6.2. Enrollment: 12 months
- 6.3. Follow-up: 12 months
- 6.4. Analysis and result report: 2 months

4. Sample size calculation for the primary analysis

4.1. Hypothesis:

This trial is a 1:1 matched comparative cohort clinical trial, with patients being assigned to either the cutting balloon or the NC balloon group (1: 1 ratio) during the study period. It will test the noninferiority of a strategy of cutting balloon pre-dilatation compared with NC balloon pre-dilatation in the treatment of calcified coronary lesion. minimal CSA at the calcium site assessed by IVUS is the primary endpoint. Limited similar clinical trials on cutting balloon for the treatment of de novo various degree calcified coronary lesions have achieved differing results. The result of a previous study that investigates the efficacy of cutting balloon indicates that the mean CSA after cutting balloon treatment for native coronary artery disease are 6.26mm and 5.03 mm in the NC balloon group (18). We hypothesize that stent implantation after the cutting balloon pre-dilatation will not be inferior to pre-dilatation with NC balloon for the treatment of de novo calcified coronary lesions. Using double-sided inspection, $\alpha = 0.05$ and $\beta = 0.2$, and considering the expected loss to follow-up of 20%, the number of cases to be included should be at least 250. Therefore, we aim for 125 cases for each group. Nevertheless, the sample size proposed was 250 patients in each group to further increase the power and account for possible protocol deviation.

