4.2. Assumption

Data for all endpoints will be evaluated using an intention-to-treat analysis. All data will be expressed as mean \pm standard deviation. The unpaired Student's t-test and Mann-Whitney U test will be used to compare continuous variables. Categorical variables will be compared using the chi-square and Fisher's exact tests. All time-to-event outcomes of MACEs will be summarized using Kaplan-Meier survival estimates and compared between the two groups using log-rank tests. $p < 0.05$ is considered statistically significant. All statistical analyses will be performed using SPSS software (version 20.0, SPSS Inc., Chicago, IL, USA).

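### Site and operator differences are not controlled in the primary comparison, and the same-operator wording in section 5.1 does not fit a five-hospital study

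*Combined protocol and SAP*

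**What the plan says.** **Who decides.** Section 5.1 under Methods (PCI procedure and medication) states: "The interventional strategy, balloon size, and stent selection will be based on the discretion of the same operator for all patients". Section 6 (Study device) also leaves the type of non-compliant (NC) balloon to the operator.

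**Where.** Section 1 (Study protocol) states "Planned number of sites: 5 institutions in South Korea" and lists hospitals in Bucheon, Cheonan, Daejeon and Seoul (two).

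**Which stent.** Section 1 describes patients "who underwent bioabsorbable polymer-coated, everolimus-eluting coronary stent implantation". Section 6 lists one stent, a "bioabsorbable polymer-coated everolimus-eluting coronary stent", with a single brand name.

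**How patients reach an arm.** Three descriptions appear: "Novel cutting balloon prospective, randomized, open-label, multi-center study" and "designed as a prospective, observational, open-label, multi-center trial" in section 1, and "This trial is a 1:1 matched comparative cohort clinical trial, with patients being assigned to either the cutting balloon or the NC balloon group" in section 4.1. No randomisation method, matching factor or stratification factor is given.

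**How the endpoint is compared.** The primary endpoint is minimal stent cross-sectional area (CSA) on IVUS at the calcium site. Section 4.2 states: "The unpaired Student's t-test and Mann-Whitney U test will be used to compare continuous variables". No site or operator term is mentioned. Section 5.3 has the IVUS recordings read offline by one observer who does not know the clinical and angiographic information.

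**The concern.** Balloon size and stent choice bear directly on the stent area achieved. The study is open-label, so operators make these choices knowing the arm. Some arrangement is therefore needed to keep differences between hospitals and operators out of the comparison of balloons.

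The sentence in section 5.1 reads as if it supplied one, because a single operator for everyone would remove operator variation. Across five hospitals it cannot be taken literally. The two usual alternatives, balancing the arms within site and adjusting for site, are not described.

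Two things are at stake. Differences between sites add noise to the unadjusted comparison. If the two balloons are also used in different proportions at different sites, those differences shift the estimated effect.

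**Working it through.** **1. Inputs from the documents.** Planning means 6.26 and 5.03 (section 4.1; printed in mm, read here as mm²), so the difference is 6.26 − 5.03 = 1.23. Two-sided α = 0.05, β = 0.2, loss 20% (section 4.1). Total 250, 125 per arm (section 4.3). Five sites (section 1). Section 4.1 also mentions 250 per group; the section 4.3 total is used here.

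**2. Inputs that are assumed.** The documents give no SD, no site means, no site sizes and no arm shares by site.

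**3. The plan's own figure.** It cannot be checked directly, because neither an SD nor a non-inferiority margin is stated. Treating 1.23 as a difference to be detected, n per arm = 2(1.96 + 0.84)² × SD² / 1.23². With SD = 3.1 this gives 100 per arm; 100 / (1 − 0.20) = 125 per arm, total 250. So 250 is reproduced only if the SD is about 3.1, a variance of 3.1² = 9.61. Multiplying by 1.20 instead of dividing by 0.80 needs an SD of about 3.17; a one-sided α of 0.05 needs about 3.50.

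**4. Precision.** Assume a between-site SD of 0.5 to 1.0 mm².
- Share of variance: 0.5² / 9.61 = 2.6%; 1.0² / 9.61 = 10.4%.
- In patients: 0.026 × 250 ≈ 7; 0.104 × 250 = 26.

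The same point in terms of an assumed intraclass correlation (ICC): replacing the SD by 3.1 × √(1 − ICC) in step 3 gives the total needed when site is adjusted for.

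| ICC | Total N |
|---|---|
| 0.01 | 248 |
| 0.05 | 238 |
| 0.10 | 226 |
| 0.20 | 200 |

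**5. Bias if arm shares differ by site.** Assume five sites of 50 patients, site means (s, s, 0, −s, −s) and cutting-balloon shares (0.6, 0.6, 0.5, 0.4, 0.4).
- Cutting arm: (30s + 30s + 0 − 20s − 20s) / 125 = 0.16s.
- NC arm: (20s + 20s + 0 − 30s − 30s) / 125 = −0.16s.
- Bias: 0.16s − (−0.16s) = 0.32s, that is 0.16 mm² at s = 0.5 and 0.32 mm² at s = 1.0.
- Against the planning difference: 0.16 / 1.23 = 13%; 0.32 / 1.23 = 26%.

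**6. How likely that pattern is under randomisation.** These site means have SD √(4s²/5) = 0.894s. Under simple 1:1 randomisation of 250 patients, the chance difference between arms in mean site effect has SD 0.894s × 2/√250 = 0.113s. The 0.32s above is 0.32 / 0.113 ≈ 2.8 SD, reached in either direction in roughly 0.5% of trials.

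**7. Type I error of the unadjusted t-test.** Simulation with 6,000 repeats per cell: five equal sites, 200 evaluable patients, assumed SD 2.0, no true difference, nominal 5%.

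| Assignment | ICC 0.05 | ICC 0.10 | ICC 0.20 |
|---|---|---|---|
| Randomised 1:1, not stratified | 4.7% | 5.4% | 4.5% |
| Randomised 1:1 within site | 4.6% | 4.1% | 3.3% |
| Cutting-balloon share 30% to 70% by site | 6.7% | 8.6% | 12.2% |

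The second row shows that stratifying while keeping the plain t-test is conservative, so stratification and adjustment belong together.

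**The case against.** The strongest reply is that the study is labelled randomised. If it is, site effects balance in expectation, the unadjusted test holds its level (step 7, top row), and the bias pattern in step 5 would be a rare accident (step 6). That stands, and under randomisation the point is about precision. It does not settle the matter, because the same document also calls the study observational and a matched cohort and describes no allocation method.

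Other points have weight:
- **Existing controls.** The PCI is to follow current guidelines and standard techniques; the cutting balloon, stent and IVUS catheter are specified; and one reader measures every recording. It would be wrong to say that the operator sentence is the only control. The single reader removes reading differences between sites, but not differences in how the procedure is done.
- **Same operator.** The phrase may mean that one operator treats both arms within a hospital. That would be a useful partial control, and a reason to clarify the sentence rather than strike it out. Differences between hospitals would still go unmodelled.
- **The SD of 3.1.** It is back-solved from a superiority-type calculation in a plan that speaks of non-inferiority. The percentages in step 4 move with it.

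Three stronger readings are tempting and not supported:
- That the operator sentence causes the lack of control. It does not; the absence of stratification or adjustment does, and would do so whatever that sentence said.
- That stents will differ between arms, so that the result could not be attributed to the balloon. Next to balloon size, stent selection may simply mean size or length, and nothing in the documents suggests a difference by arm.
- That the trial is 7 to 26 patients short. If 3.1 is a total SD, variation between sites is already inside the 250, and those patients are efficiency given up.

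**Conclusion.** The point holds in two separate parts.

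The first is wording. One operator for all patients does not fit five hospitals when read literally. Open stent selection beside a single listed stent is an ambiguity to reconcile, not a proven contradiction.

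The second is method. As written, neither the assignment nor the primary analysis takes account of site or operator. With genuine 1:1 randomisation the consequence is a modest loss of precision, a few per cent to about a tenth of the variance under the assumptions in step 4. With non-random or site-uneven assignment the estimate is also biased, by 0.16 to 0.32 mm² in the illustration, and the false-positive rate rises above 5%. The direction of any bias is unknown.

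Which case applies cannot be told from the documents. All sizes depend on assumed site means, arm shares and ICCs, and the variance shares also on the back-solved SD. Adjusting for site removes differences between sites only; if assignment is not random, selection of patients within a site would remain.

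**What to change.** - State how patients are assigned, resolve the three design descriptions, and stratify the 1:1 assignment by site.
- Make the primary analysis of minimal stent CSA a linear model with arm and site as factors (for example ANCOVA in place of the plain t-test), reporting the adjusted difference with its confidence interval.
- Record the operator and the stent type used for every patient.
- Reconcile section 5.1 with section 1 on who operates, for example whether the same operator treats both arms within a site, and with sections 1 and 6 on what stent selection covers given the single study stent. The clinical content of that reconciliation is for the investigators.

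The cost is a stratified allocation list, two recorded data items, a wording correction and one extra model factor using four degrees of freedom. No increase in sample size is needed: under the assumptions in step 4, the total required with site adjustment is 250 or lower.

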7.2. Exclusion criteria

- 1) extremely tortuous or angulated lesions,
- 2) lesions with dissection before balloon pre-dilatation,
- 3) lesions within the vein graft,
- 4) extremely narrow lesions which need rotational atherectomy,
- 5) ST-elevation myocardial infarction (STEMI).
- 6) Comorbidities that preclude the achievement of one-year follow-up.

8. Expected study period

- Enrollment: 12 months
- Follow-up: 12 months
- Data analysis: 2 months
- Publication including target journal and presentation:
JACC: Cardiovascular Interventions
Circulation: Cardiovascular Interventions
TCT 2025

9. Safety Reporting including DSMB

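### Section 5.1 excludes balloon-uncrossable lesions without saying whether the balloon has already been assigned; if it has, the exclusion can differ by arm and conflicts with intention-to-treat

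*Combined protocol and SAP*

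**What the plan says.** Five parts of the combined protocol and SAP bear on this.

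- **5.1, PCI procedure and medication.** Rotational atherectomy may be used at the operator's discretion "in cases of balloon-uncrossable lesions, and these cases will be excluded from enrollment". The same paragraph says: "The interventional strategy, balloon size, and stent selection will be based on the discretion of the same operator for all patients".
- **7.2, Exclusion criteria, item 4.** The related eligibility rule covers "extremely narrow lesions which need rotational atherectomy". It does not say when or how this need is judged. Item 2 of the same list, on dissection, is tied to the time before pre-dilatation.
- **4.1, Hypothesis.** The only timing given for allocation is "with patients being assigned to either the cutting balloon or the NC balloon group (1: 1 ratio) during the study period".
- **4.2, Assumption.** "Data for all endpoints will be evaluated using an intention-to-treat analysis".
- **5.3, IVUS procedure and analysis.** "IVUS will be performed at baseline (before pre-dilatation) and repeated immediately after stent implantation in all cases".

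The opening of the protocol describes the trial as "Novel cutting balloon prospective, randomized, open-label, multi-center study". Section 6 lists two pre-dilatation devices, the cutting balloon and an NC balloon of the operator's choosing. No common balloon for a crossing test before assignment is described.

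**The concern.** The pre-dilatation balloon is the treatment under comparison. If it has been assigned when the operator tries to cross, failure to cross is partly a result of that assignment. Removing the patient at that point is then an exclusion made after allocation, by someone who knows the arm, and triggered by the performance of the assigned device.

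Three things would be at stake.

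- **Comparability.** If the two balloons cross at different rates, the arm with the poorer crosser loses more of its difficult lesions and keeps the easier ones. Its mean minimal stent area then looks better than it should. If that arm were the cutting balloon, the error would favour the noninferiority claim.
- **Completeness.** Failure to cross is itself a device outcome, and it would drop out of the results. Procedure time, contrast volume and number of balloons, all secondary endpoints, would lose the same cases.
- **Planned numbers.** The 20% allowance in 4.1 is for loss to follow-up. Nothing is set aside for removals during the procedure.

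**Working it through.** **Step 1: the order of events.** 5.3 puts angiography and baseline IVUS before pre-dilatation. 5.1 makes its exclusion turn on a balloon failing to cross. 4.1 does not place assignment anywhere in this sequence. Two readings remain:

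| Order | Status of the 5.1 exclusion | Intention-to-treat (4.2) |
|---|---|---|
| Crossing settled, then assignment | Eligibility rule; patient never enrolled | No conflict |
| Assignment, then crossing attempt | Post-assignment exclusion, may differ by arm | Conflict |

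The first reading would need some way of settling crossability before either study balloon is used, and none is described. The second would need assignment before the attempt, and that is not stated either.

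**Step 2: the plan's own figure.** 4.1 gives means of 6.26 and 5.03 (printed in mm; an area would be in mm²), so a difference of 1.23. It also gives two-sided α 0.05, β 0.2 and 20% loss. Section 4.3 gives 250 in total, 125 per arm. No SD and no noninferiority margin are stated, so 250 cannot be reproduced. Solving for the SD that would give it, with 125 × 0.8 = 100 evaluable per arm:

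SD = 1.23 × √(100/2) / (1.960 + 0.842) ≈ 3.10

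This is an inferred value and is used below only as a scale.

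**Step 3: illustrative bias, simple form.** Let p be the share removed in each arm and D the mean stent area of retained lesions minus that of removed lesions, taken as equal in both arms. Then

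bias in the difference (cutting − NC) = (p_cut − p_NC) × D

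- Low: (0.03 − 0.01) × 1 = 0.02 mm²
- High: (0.10 − 0.03) × 2 = 0.14 mm²

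The rates and D are assumptions. This form does not need the SD.

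**Step 4: illustrative bias, hardest lesions removed.** Suppose the hardest share p is removed on a normal difficulty score that has correlation −r with stent area. The retained mean rises by r × SD × g(p), where g(p) = φ(z)/(1 − p) and z is the upper p quantile. The values are g(0.01) = 0.0269, g(0.02) = 0.0494, g(0.03) = 0.0701, g(0.05) = 0.1086 and g(0.10) = 0.1950. The bias is r × SD × [g(p_cut) − g(p_NC)]. With SD 3.1:

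| Removed, cutting vs NC | r = 0.3 | r = 0.5 |
|---|---|---|
| 3% vs 1% | 0.04 mm² | 0.07 mm² |
| 5% vs 2% | 0.06 mm² | 0.09 mm² |
| 10% vs 3% | 0.12 mm² | 0.19 mm² |

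This is 3% to 16% of 1.23. With SD 2.0 the extremes scale by 2.0/3.1, to about 0.03 and 0.12 mm².

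**Step 5: context.** At SD 3.1 the standard error of the difference is 3.1 × √(2/100) = 0.44 mm² with 100 per arm, or 3.1 × √(2/125) = 0.39 mm² with 125. The largest bias above is just under half a standard error (0.19/0.39); the smallest is about 0.05 of one (0.02/0.44). If assigned patients were removed without replacement, 10% against 3% of 125 would be 12.5 against 3.75 patients.

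**Step 6: direction.** Equal shares and equal D give zero. Swapping the two rates changes the sign, and the bias then works against the cutting balloon.

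**The case against.** The strongest reply is that the rule speaks of exclusion from enrolment, not of withdrawal after assignment or omission from the analysis. Criterion 4 in 7.2 already lists the need for rotational atherectomy as an eligibility exclusion, and 5.1 may only restate it. Intention-to-treat says nothing about people who were never enrolled. This stands: a reader might infer that the plan contradicts its own intention-to-treat statement outright, but the documents do not put assignment before the crossing attempt, so the conflict is conditional.

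A second reply is that a partial screen exists. In 5.3 the IVUS catheter is passed beyond the culprit lesion before pre-dilatation in every case, and inclusion criterion 2 names IVUS among the means of confirming calcium. Some of the tightest lesions would therefore be recognised before either study balloon is used. This also stands in part, and it makes the hardest-lesion calculation an upper-end picture. But passage of an IVUS catheter does not establish that a balloon will cross, and 5.1 makes balloon crossing the test.

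A third reply is that the magnitudes have no basis in the documents. That is correct for the rates, the shortfall in area, the correlations and the direction, and the SD is inferred. A reader might also infer that the rule favours the cutting balloon; nothing in the documents says which balloon crosses less often. Nor do they show that patients would be lost from the 125 per arm: if exclusion precedes enrolment, recruitment simply continues.

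What the replies do not remove is the gap itself. In an open-label trial with strategy, balloon size and NC balloon type left to the operator, a rule triggered by a balloon attempt needs a stated position relative to assignment.

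**Conclusion.** The point holds as a conditional one. As written, 5.1 can be applied so that patients leave the trial according to the balloon they were assigned, and nothing in the protocol prevents this. If assignment comes first, the exclusion conflicts with 4.2; if crossability is settled first, it does not.

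The size is unknown. Under the assumed rates the bias runs from about 0.02 to 0.19 mm² against a planning difference of 1.23. It is modest beside the sampling error, zero under balance, and of either sign. Because no noninferiority margin is stated, it cannot be shown to be negligible against one. The finding rests on the missing order of events, not on these figures. It should be corrected, but it does not by itself invalidate the design.

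**What to change.** Changes to the protocol text:

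1. State that assignment takes place only once eligibility is final and the baseline IVUS run, already planned in all cases, is complete.
2. Apply the uncrossable/atherectomy exclusion only before assignment.
3. Keep every assigned patient in the intention-to-treat set and count the final minimal stent area whatever device was used afterwards. Say how an assigned patient who receives no stent, and so has no primary endpoint, will be handled.
4. Report failure to cross by arm, with the numbers screened, assigned and found uncrossable.
5. Reconcile 5.1 with exclusion criterion 4 in 7.2, so that one rule with one time of assessment applies.

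None of this alters the operator's clinical discretion, including over atherectomy. The cost is wording plus simple counts, with no added procedure or measurement. The downside is that a few difficult cases stay in the analysis, so the result may be slightly less favourable.

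### Section 5.1 (PCI procedure and medication): the maintenance sentence gives prasugrel at the section's own loading amount, 60 mg, with no frequency; for ticagrelor the frequency and division are missing

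*Combined protocol and SAP*

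**What the plan says.** Section 5.1 (PCI procedure and medication; the number 5.1 is also used for the primary endpoint) lists the same four antiplatelet drugs with amounts twice.

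- Before PCI: "all patients will be administered loading doses of aspirin (200–300 mg), clopidogrel (300–600 mg), ticagrelor (180 mg), or prasugrel (60 mg").
- After PCI: "All patients who undergo PCI will receive aspirin (100 mg daily) with clopidogrel (75 mg daily), ticagrelor (180 mg), or prasugrel (60 mg"). The reason given in the same sentence is that a dual antiplatelet "maintenance regimen for at least 12 months is recommended".

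The next sentence adds an optional drug with both amount and frequency: "Cilostazol (100–200 mg daily) will be administered as an adjunct to the dual antiplatelet regimen". Later in the section ticagrelor and prasugrel appear again in the list of in-hospital and after-discharge medications to be recorded, by name only.

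The section opens with a reference to guidelines: "PCI and stent implantation will be performed according to the current guidelines using standard interventional techniques". The subject of that sentence is the procedure and the stent, not drug dosing.

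**The concern.** The second list is an instruction for maintenance treatment, yet its prasugrel entry is the amount that the first list calls a loading dose, and it carries no frequency. A site that works from the protocol alone has two ways to read it. Either the daily marking on the neighbouring drugs is meant to extend to prasugrel, which puts patients on the loading amount every day for at least 12 months, or it is not, and the protocol gives no schedule.

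Ticagrelor raises a smaller question. Its amount is also unchanged and its frequency is also absent, but 180 mg could be the total for a day.

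Two things are at stake. One is patient safety, if the prasugrel entry is followed as it stands. The other is an executable protocol: under section 9.2 the trial monitor examines compliance with the protocol, and deviations go to the executive committee and principal investigator within 7 days, but for these two drugs there is no complete regimen to check against.

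**Working it through.** No sample-size or power calculation bears on this point. The check sets the two lists side by side and then looks for a repair elsewhere in the document.

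**Inputs**, all from section 5.1 (PCI procedure and medication):

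| Drug | Loading amount | Amount in maintenance sentence | Frequency in maintenance sentence |
|---|---|---|---|
| Aspirin | 200–300 mg | 100 mg | daily |
| Clopidogrel | 300–600 mg | 75 mg | daily |
| Ticagrelor | 180 mg | 180 mg | none |
| Prasugrel | 60 mg | 60 mg | none |

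**Step 1. Ratio = maintenance amount / loading amount.**

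- Aspirin: 100/300 = 0.333 to 100/200 = 0.50.
- Clopidogrel: 75/600 = 0.125 to 75/300 = 0.25.
- Ticagrelor: 180/180 = 1.00.
- Prasugrel: 60/60 = 1.00.

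The two entries with a ratio of 1.00 are the same two of four that lack a frequency. The ratios describe the inconsistency in the text; they do not measure harm.

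**Step 2. The two readings.**

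- *Daily is read through the list.* Prasugrel becomes 60 mg per day, 1.00 times its loading amount on every day of the regimen. Ticagrelor becomes 180 mg per day, which is a coherent entry if 180 mg is a daily total, with the division still unstated.
- *Daily applies only where it is printed.* Neither drug has a schedule.

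Prasugrel needs an answer from the investigators under both readings. Under the first reading ticagrelor needs only the division of the dose; under the second it also needs the frequency.

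**Step 3. Does another place settle it?**

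- The cilostazol sentence gives amount and frequency, so the section's pattern for a continuing drug is to state both. It gives nothing for the other two drugs.
- The list of recorded medications has no amounts.
- The guideline sentence covers the procedure and stent implantation.
- No other section gives a dose of either drug.
- A page break splits the maintenance sentence, but it falls after the four doses and hides none of them. There is no sign of redaction.

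**Step 4. Does it reach the primary endpoint?** The primary endpoint is minimal stent cross-sectional area at the calcium site on IVUS. Section 5.3 (IVUS procedure and analysis) has the imaging "repeated immediately after stent implantation in all cases", before any long maintenance course. The maintenance sentence is worded identically for both arms.

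**The case against.** The strongest case on the other side has four parts.

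1. **Carry-over from the loading list is an inference.** The documents show that two amounts fall and two do not. Nothing in them says that a maintenance amount must be lower than a loading amount, and they do not give the intended values. This stands. What the documents establish is the repetition of the amount and the missing frequency, not how it came about or which number is right.

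2. **The ticagrelor entry may be correct.** This stands too. A reader might infer that both drugs carry a loading dose into maintenance. For ticagrelor the documents do not support that, because 180 mg can be read as a daily total.

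3. **The sentence does not literally order a year of daily loading doses.** A reader might infer that it does. That needs the daily marking to extend across separate parentheses, although it is printed individually for aspirin and clopidogrel. The clause that presents the regimen as recommended care also makes that outcome less plausible, and physicians may well dose from outside guidance. This lowers the chance that anyone is dosed that way. It does not supply a dose, and the other reading leaves prasugrel without a schedule.

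4. **It is background therapy with little weight for the trial's results.** Agreed. A reader might go on to infer a bias in the 1-year MACE or TLR comparison. The documents do not support that: the wording is common to both arms, and nothing says how many patients will take either drug.

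None of the four parts removes the need to complete the entries.

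**Conclusion.** The point holds as an internal inconsistency, not as a criticism of a design choice. For prasugrel, the maintenance sentence states 100% of the section's own loading amount and no frequency, so neither available reading gives a usable instruction that is clearly a maintenance dose. For ticagrelor, what is shown is narrower: frequency and division are not stated.

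The correction should be made, on grounds of patient safety and executability only. The conclusion rests on the text of section 5.1 and on the absence of a dose for either drug anywhere else. It does not rest on knowledge of what the correct doses are. The documents do not show that either amount is harmful, and they give no expected use of either drug, so no patient count can be attached. Nothing here changes the primary endpoint, power, alpha or the comparison between arms.

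**What to change.** Edit the maintenance sentence of section 5.1 (PCI procedure and medication) and nothing else:

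- **Prasugrel:** replace the entry with 'prasugrel ([amount], [frequency])', the values to be confirmed by the clinical investigators.
- **Ticagrelor:** state whether 180 mg is the daily total and how it is divided; if it is not, give the confirmed amount and frequency.

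Then send a notice of the corrected sentence to the sites; section 1 plans for five ("Planned number of sites: 5 institutions in South Korea"). This review does not propose the values.

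The cost is two entries in one sentence and one notice. Endpoints, sample size, visits and analysis stay as they are.
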